Secondary Objectives:

Device success, procedural success, angioplasty outcomes, MACE at 6/12 months, TLR at 6/12 months, SAEs, MACE-free survival.

Endpoints:

Primary Endpoint:

MACE at 30 days.

Secondary Endpoints:

Device success, procedural success, post-usage angioplasty results, MACE at 6/12 months, TLR, TVR, SAEs, MACE-free survival.

Study Population:

Sample Size: 360 subjects

Inclusion/Exclusion criteria:

Inclusion Criteria:

Those subjects eligible for and who met the following inclusion/exclusion criteria were enrolled in this study.

1. Adults ≥ 18 yrs,
2. Clinical indication for PCI
3. suitable lesion for DCB-only strategy
4. small vessel disease
5. Patient has clinical evidence of ischemic heart disease or a positive functional study
6. Patient and his or her treating physician agree that the patient will comply with all the required post-procedure follow-up.

7. One or more target lesions require treatment

Exclusion Criteria:

Patients were excluded if **ANY** of the following conditions apply:

1. Patient has active infection
2. STEMI <72 hrs, LM disease,
3. heavy calcification, thrombus-rich lesions,
4. mandatory stent requirement,
5. sirolimus allergy, pregnancy,
6. Concurrent medical condition with a life expectancy <1 yr
7. Clinically relevant contraindication to aspirin, heparin, clopidogrel bisulphate, or ticlopidine including thrombocytopenia, neutropenia, or leukopenia
8. Active peptic ulcer or upper gastrointestinal bleeding.
9. Current participation in an investigational drug or device trial that has not completed its primary endpoint follow-up period.
10. Pregnancy or woman of childbearing potential who, in the opinion of the investigator, does not take adequate measures to prevent conception

Study Design:

Comparative Arm: None (no randomization)

Centers: Multicenter – Malaysia, Myanmar

Study Duration: 12 months follow-up per patient

Introduction

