The Mamba Rapid Exchange Sirolimus Coated Dilatation Catheter is a rapid exchange, PTCA catheter with a balloon located at its end designed for Transluminal angioplasty by percutaneous way. This catheter includes distally two coaxial lumens with a balloon located at the tip. One lumen is used for inflation of the balloon and the other permits the use of guide wire (0.014" max) to facilitate the advancement of the catheter to and through the stenosis to be dilated. The MAMBA Rapid Exchange Sirolimus Coated Dilatation Catheter has flexible distal shaft with a hydrophilic coating on its outer body. The balloon has two Platinum-Iridium radiopaque marker bands, one at each end of the balloon, which represents the approximate balloon working length at nominal pressure for correctly positioning the balloon under fluoroscopy.

Mamba is a Sirolimus Coated Dilatation Catheter for the treatment of coronary artery disease, indicated for In-Stent Restenosis, Small Vessels and Bifurcation Lesions. Sirolimus Coated Dilatation Catheter (DCB) is a novel device for Percutaneous Coronary Intervention (PCI), which has demonstrated favorable outcome due to its peculiar characteristic of a high-concentration, rapid local delivery of an anti-restenotic drug without the use of a durable polymer or metal stent.

[figure not shown]
Drug Sirolimus

[figure not shown]
Mamba Sirolimus Drug Eluting PTCA Catheter has a drug loading of 2.75 $\mu\text{g}/\text{mm}^2$ of balloon surface area coated with Sirolimus as the active anti-proliferative agent.

Mechanism of Action for Sirolimus:

The mechanism by which the Sirolimus Coated Dilatation Catheter inhibits neointimal growth as seen in pre-clinical and clinical studies has not been established. At the cellular level, Sirolimus inhibits growth factor-stimulated cell proliferation. At the molecular level, Sirolimus forms a complex with the cytoplasmic protein FKBP-12 (FK 506 Binding Protein). This complex binds to and interferes with FKBP-12 Rapamycin Associated Protein (FRAP), also known as the mammalian target of rapamycin (mTOR), leading to inhibition of cell metabolism, growth, and proliferation by arresting the cell cycle at the late G1 stage.

It inhibits growth factor & cytokine-stimulated cell proliferation. DNA damage checkpoint (G1 check):chk1-kinase inactivation before DNA replication and also inactivation of cdk2- cyclin a protein (growth factor).

Balloon

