A balloon is made up of nylon material having PTFE coated stainless steel hypo tube shaft. Two radiopaque markers located underneath the balloon, fluoroscopically mark the working length of the balloon.

Available Sirolimus Drug Eluting PTCA Catheter Sizes

Diameters (mm)	Available Lengths (mm)									
1.50	06	08	10	12	15	20	25	30	35	40
2.00	06	08	10	12	15	20	25	30	35	40
2.25	06	08	10	12	15	20	25	30	35	40
2.50	06	08	10	12	15	20	25	30	35	40
2.75	06	08	10	12	15	20	25	30	35	40
3.00	06	08	10	12	15	20	25	30	35	40
3.50	06	08	10	12	15	20	25	30	35	40
4.00	06	08	10	12	15	20	25	30	35	40

Study rationale

This is a multi-center; prospective study aimed at evaluating the safety and effectiveness of the Mamba Sirolimus Drug Eluting PTCA Catheter in reducing neointimal hyperplasia and decreasing restenosis during PCI of stenotic coronary artery disease as well as intermediate-term outcomes. High Radial Strength, Excellent conformability, and Sirolimus eluting characteristics. A Drug Eluting PTCA Catheter of this type is expected to decrease restenosis following PCI and thereby improve Clinical Outcomes.

Study Procedure:

Baseline evaluation, index PCI procedure, device success, procedural success, post-angioplasty results. Follow-up at 1, 6, 12 months (clinical only).

Screening and eligibility check

Informed consent

Baseline assessment (demographics, ECG, labs, angina class)

Index DCB procedure (balloon angioplasty using Sirolimus-coated DCB)

Pre-dilatation of the target lesion with an appropriate semi-compliant or non-compliant balloon is mandatory. Only lesions with successful pre-dilatation—defined as TIMI 3 flow, no flow-limiting dissection, and $\leq 30\%$ residual stenosis—are eligible for DCB deployment."

No stent implantation unless medically necessary (bailout)

Discharge as per hospital protocol

Follow-up visits at 1, 6, and 12 months for clinical evaluation, ECG, and adverse event assessment

Follow-Up Schedule:

Timepoint	Visit Type	Assessments
Day 0	Baseline	Demographics, consent, eligibility, angina class, ECG, labs
Day 1	Procedure	DCB implantation, procedural outcomes
1 Month	Clinic visit	MACE, adverse events, ECG, medication adherence
6 Months	Clinic/Tele	MACE, TLR, adverse events, angina class
12 Months	Final visit	MACE, TLR, SAE reporting, device durability

Data Management and Monitoring:

Use of Electronic Data Capture (EDC)

On-site and remote monitoring

Centralized adjudication of endpoints by Clinical Events Committee (CEC)

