MACE (Major Adverse Cardiac Events):

Composite of Death (Both Cardiac & Non-Cardiac Death), MI (Q-wave and Non-Q-wave), (emergent)

CABG or clinically driven Target Lesion Revascularization (TLR).

Major vascular complications:

All pseudoaneurysms, vascular access site bleeding associated with a decrease in hemoglobin ≥ 3.0 mmol/L as well as vascular events which required surgical repair or transfusion of > 2 units within 30 days of the procedure.

MI (Myocardial Infarction):

Necrosis of the myocardium, as a result of interruption of the blood supply to the area, as in coronary thrombosis.

MI, non-Q-Wave:

Elevation of post-procedure CK levels to > 2 times normal with elevated CK-MB in the absence of pathological Q waves. If no assay for CK-MB was performed, elevation of CK levels to > 2 times normal without new Q waves is also considered a non-Q-wave MI.

MI, Q-Wave:

MI, Q-Wave Development of new, pathological Q waves in 2 or more contiguous leads (as assessed by the investigator and confirmed by the Clinical Endpoint Committee) with post-procedure CK-MB levels elevated above normal.

MLD (Minimal Lumen Diameter):

MLD (Minimal Lumen Diameter) Mean Minimal Lumen Diameter (mm).

Procedure success rate: Percentage of patients with angiographic success and without the occurrence of MACE during the index hospitalization.

QCA (Quantitative Coronary Angiography, off-line):

Off-line refers to assessment at the Angiographic Core Laboratory. The method is a quantitative estimate obtained with a digital angiographic computer utilizing an automatic edge detection algorithm.

RVD (Reference Vessel Diameter):

Interpolated reference diameter.

SAE (Serious Adverse Event):

An adverse event is defined as serious, whenever the adverse event is fatal, life-threatening, results in persistent or significant disability/incapacity, requires inpatient hospitalization or prolongation of hospitalization, results in fetal death or distress, is a congenital anomaly/birth defect and in cases of cancer/malignancy.

Stroke:

A focal neurological deficit, resulting from a vascular cause involving the CNS, of sudden onset that is not reversible within 24 hours (including death) and which is not due to a readily identifiable cause (i.e. brain tumor, trauma).

TLR (Target Lesion Revascularization):

Any repeat treatment of the stented segment including 5 mm proximal and 5 mm distal from the edge of the stent.

TVF (Target Vessel Failure):

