Cardiac Death, MI (Q-wave and non-Q-wave) or Target Vessel Revascularization (TVR) that could not be clearly attributed to a vessel other than the target vessel.

TVR (Target Vessel Revascularization):

Revascularization of any segment of the index coronary artery, which was in physical contact with any component (guiding catheter, guidewire, balloon catheter, etc.) of the angioplasty hardware during the initial procedure

TWS (Technician's Work Sheet):

Part of the CRF used to specify the details of the angiographic procedure and the angiographic observations.

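### TLR is defined by a stented segment and a stent edge, but the trial is designed to leave no stent, so the definition cannot count repeat treatment of an unstented target lesion

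*Protocol*

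**What the plan says.** Appendix I of the Protocol defines TLR as "Any repeat treatment of the stented segment including 5 mm proximal and 5 mm distal from the edge of the stent". No other definition of TLR appears in the document.

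The treatment plan points the other way:

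- Inclusion criterion 3 asks for a "suitable lesion for DCB-only strategy".
- Exclusion criterion 4 removes patients with a "mandatory stent requirement".
- Study Procedure states "No stent implantation unless medically necessary (bailout" as the only exception.
- The Introduction describes the device as "indicated for In-Stent Restenosis, Small Vessels and Bifurcation Lesions". A pre-existing stent at the target lesion is therefore possible. The exclusion criteria do not rule it out, although small vessel disease is listed as an inclusion criterion.

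TLR enters the results in two ways. The MACE definition in Appendix I includes clinically driven TLR alongside death, MI and emergent CABG. MACE is the primary endpoint at 30 days and a secondary endpoint at 6 and 12 months. TLR is also a secondary endpoint in its own right.

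Target vessel revascularization (TVR) is defined differently: "Revascularization of any segment of the index coronary artery, which was in physical contact with any component" of the angioplasty hardware, with the balloon catheter named among the examples. TVR is not a MACE component.

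**The concern.** A TLR rule needs a segment and an edge from which to measure its 5 mm margins. For a lesion treated with the balloon alone, this definition supplies neither. Read literally, repeat treatment of such a lesion can never be a TLR, however clearly the treated site has re-narrowed.

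Two outcomes are possible, and neither is satisfactory:

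- If the wording is followed, TLR and the TLR part of MACE are undercounted in unstented lesions, and the device looks better than it is.
- If the Clinical Events Committee improvises, it must choose among the lesion, the pre-dilated length and the drug-coated balloon length. The choice may differ between cases, and the bias could go either way.

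The study rationale is reduced restenosis, and follow-up is clinical only. Repeat revascularization of the treated lesion is therefore the endpoint closest to what the study wants to show. With no hypothesis test planned, the MACE rate with its 95% CI and the TLR rate are themselves the result.

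**Working it through.** **Step 1. Which lesions can the definition reach?** The protocol states no figure to reproduce, so the first check is to go through the lesion types.

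| Target lesion | Stented segment present? | Can a TLR be counted as written? |
|---|---|---|
| Balloon only, no prior stent (the planned treatment) | No | No |
| Bailout stent placed at the index procedure | Yes | Yes |
| In-stent restenosis, if enrolled | Yes (older stent) | Yes |

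The definition works only for the exception and for a subgroup whose enrolment is not clearly settled.

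**Step 2. Which endpoints are affected?** These are MACE at 30 days (primary), MACE and TLR at 6 and 12 months, and MACE-free survival. Procedure success is also touched, because Appendix I makes it depend on in-hospital MACE. Death, MI and emergent CABG are counted either way. A missed TLR lowers patient-level MACE only if the patient has none of these in the same window. Missed events would normally still appear under TVR.

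**Step 3. Illustrative size under literal use.** From the protocol: N = 360. Assumed, because the protocol gives neither: the true TLR rate *t*, and the share *s* of patients with a stent at the target lesion (bailout or pre-existing), taken as 0.05 to 0.50. TLR risk is assumed equal with and without a stent.

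Missed = 360 × *t* × (1 − *s*)

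| Window | Assumed *t* | True events | Missed, *s* = 0.50 | Missed, *s* = 0.05 |
|---|---|---|---|---|
| 30 days | 0.5% | 1.8 | 0.90 | 1.71 |
| 30 days | 1.0% | 3.6 | 1.80 | 3.42 |
| 12 months | 3% | 10.8 | 5.40 | 10.26 |
| 12 months | 5% | 18.0 | 9.00 | 17.10 |
| 12 months | 8% | 28.8 | 14.40 | 27.36 |

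- 30 days: 0.90/360 = 0.25 to 3.42/360 = 0.95 percentage points of MACE at most.
- 12 months: 5.40/360 = 1.5 to 27.36/360 = 7.6 percentage points of TLR.
- At a true 12-month TLR of 5% (18 events), 18 × 0.05 = 0.9 to 18 × 0.50 = 9.0 events would be counted, a reported rate of 0.25% to 2.5%.

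**Step 4. Comparison with sampling error (Clopper–Pearson, N = 360).**

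- 9/360 = 2.5%: 95% CI 1.15–4.69%. The 30-day shift of at most 0.95 points is small beside this.
- 18/360 = 5.0%: 95% CI 2.99–7.79%.
- 0/360, the limiting case with no stent in any patient: 95% CI 0–1.02%. This does not overlap the interval for 18/360, so at 12 months literal use could change the reported picture.

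**The case against.** The best reply is that the intended meaning is easy to guess. The term being defined is target lesion revascularization, and elsewhere the protocol uses target lesion for whatever is treated. Its list of anticipated events also mentions restenosis of a stented segment as a complication of this balloon procedure, which suggests wording carried over from a stent protocol. Data Management and Monitoring provides for "Centralized adjudication of endpoints by Clinical Events Committee (CEC"), and a competent committee would hardly record zero TLR in every unstented lesion. Missed events would still show up as TVR, no test turns on the result, and every rate used for the size is assumed.

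Much of this stands. Literal application is the less likely branch, so the counts above describe a possible error, not a forecast. They also depend heavily on the assumed stent share: if only 0–20% of TLR events fell in stented lesions, 80–100% would be missed, against 50–95% under the 5–50% range used here. The effect on the primary endpoint is small in any case.

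The objection does not remove the defect. The protocol never states the intended reading, gives the committee no other rule, and leaves open which length and which edge carry the 5 mm margins. TVR keeps the events in the data but does not return them to MACE. Nor is this a detail properly left to a statistical analysis plan: the protocol states a rule, and the rule does not fit the intervention.

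**Conclusion.** The concern holds. The only TLR definition does not fit a balloon-only strategy and gives no usable segment for an unstented target lesion. Followed literally, it undercounts TLR and the TLR part of MACE. Interpreted freely, it leaves the endpoint to case-by-case judgement, with error of unknown direction.

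The true size cannot be computed from the protocol. On the assumptions shown, the 30-day primary endpoint would lose at most 0.25–0.95 percentage points, which is minor. The exposure is mainly in 12-month TLR and MACE, where literal use could remove half or more of the TLR events. This should be fixed. It does not invalidate the design, and no pass/fail decision depends on it.

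**What to change.** Replace the TLR sentence in Appendix I with a definition tied to the treated segment. For example: repeat revascularization (PCI or bypass) of the target lesion, meaning the segment treated with the study balloon, together with any bailout or pre-existing stent at that lesion, and 5 mm proximal and distal to the edges of that segment. If the sponsor prefers not to extend the segment to a pre-existing stent beyond the balloon-treated length, the text should say so. The essential change is to the anchor.

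Keep the clinically driven subset as the MACE component and continue to report TLR separately. Put the same wording in the Clinical Events Committee's instructions before adjudication starts.

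The cost is one sentence in the protocol and the matching committee text, with no extra patients or visits. The position and length of the balloon-treated segment must reach the committee from the procedure record. The technician's work sheet described in Appendix I already covers details of the angiographic procedure and may supply this.
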